Figure 1 charts the study protocol and randomization.

[figure not shown]

Figure 1: Flowchart of the protocol. After consent, the subject is randomized to the order of low and standard of care dose PET/CT. If the patient opts out of the second whole-body sweep, both exams will be performed at 75 min +/- 10 min p.i., otherwise the 1st sweep will be performed at 60 min +/- 10 min, followed by the 2nd at 75 min +/- 10 min.

Sample Size Considerations

The project statistician has calculated a required sample size of 33 evaluable subjects per imaging modality if we assess tracer uptake (FDG) using both a quantitative (SUVmax) and a visual quality assessment. Based on the literature and our preliminary work, we assume that the coefficient of variation (COV) is 12% and the equivalence limit is 10%. With a total sample size of 33 patients we will achieve 80% power in an equivalence test of means using two one-sided tests (TOST) on data from a two-period cross-over design, using an alpha level of 0.025 (0.05/2) after Bonferroni adjustment each system, respectively. We assume a drop-out rate of 10% (4 subjects) which leads to our target population of 37 enrolled subjects per unique sub-study.

Four imaging systems will be utilized in this study:

- Gemini TOF Astonish system from Philips Healthcare Cleveland
- Biograph mCT from Siemens Knoxville
- Discovery PET/CT from General Electric, Milwaukee
- Vereos 128 PET/CT from Philips Healthcare Cleveland (this is the first commercial digital PET detector system)

The subjects imaged at each of the four PET/CT systems will treated as its own sub-study. Each sub-study will follow the same imaging protocol.

We will evaluate four different state of the art PET/CT system in the above defined six sub-studies which then leads to the overall study population estimate of 204 subjects.

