Participants in the research imaging will be predominately recruited from patients seen at the OSU Wexner Medical Center, including its outpatient facilities. Flyers will be available to patients that are seen in clinic offices typically referring patients for PET/CT examinations. This study will be published at clinicaltrials.gov. Potential participants will be identified by study team members at the time of the patient's standard of care imaging procedure. The patient population will include a variety of disease entities; therefore, enrollment will be monitored for relative distribution across disease categories, and the Principal Investigator's discretion will be utilized regarding the number of patients enrolled and their disease types in order to ensure a representative sample.

Randomization: Patients will be randomized in a 1:1 ratio to receive either standard of care FDG PET/CT dosing (481 MBq [13 mCi]) followed by the low dose FDG PET/CT (185 MBq [5 mCi]), or the low dose FDG PET/CT followed by the standard of care dosing using a randomized permuted block scheme in a blinded fashion. The block sizes will not be known to the investigator. No stratification factor will be included. We will, however, have the option of a randomization waiver if there are reasons that would otherwise delay patient care or prevent the patient from participating in the study.

Inclusion Criteria:

- Male and female patients greater than or equal to 18 years of age.
- Patients scheduled for a standard of care PET/CT scan.
- For female patients of child-bearing potential, the OSUWMC requirements for receiving the standard of care PET imaging agent and CT examination need to be met.

Since the patient will receive a standard of care scan as part of the protocol, we will follow the OSUWMC Imaging Services Departmental Policy and Procedure, which states that all females of child-bearing age (12-55 years old), will receive urine HCG pregnancy testing within seven days prior to imaging. While the policy also states that patients may refuse the testing by completing the pregnancy testing refusal form, we will not accept the form for this trial. All female patients of child-bearing age will be required to have the urine HCG test on the day of imaging or no more than 7 days prior to the imaging.

Exclusion Criteria:

- Participants who are pregnant or lactating.
- Prisoners.
- Participants incapable of giving informed consent.

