- Patients unable to lie flat on the scanner for extended periods of time.

Measurement / Instrumentation

Our assessment approaches will be guided by recent community efforts established via the QIBA (RSNA) effort, PET recommendations (SNM), the QIN (NCI) and IROC (NCTN).

In this study, we will not evaluate the impact of the CT-based attenuation scan, as in recent years extensive efforts in CT dose reduction have also translated to substantially lower CT doses for attenuation scans, unless diagnostic read quality is needed to simultaneously replace an additional diagnostic CT scan. We will perform all CT-based attenuation scans at the lowest dose we established for our standard of care PET/CT protocol for each specific PET/CT system.

We currently have four different state of the art PET/CT systems within the OSU Wexner Medical Center. We therefore plan to perform this trial in four separate sub-studies, each being independent for each device, with everything else being standardized. With this unique ability to evaluate the dose and timing impact and to prove equivalency using four distinct platforms in parallel, we will achieve the most meaningful outcome and impact. This will allow us to achieve the desired changes of reducing radiation dose and enabling more flexibility in the imaging time post injection.

The imaging data will be assessed in a fully blinded fashion. Our primary endpoint will be the statistical confirmation that the SUV max measured in the regions of interest (ROI) in the target region will reveal a variation of less than 10%. The project statistician has calculated a required sample size of 37 evaluable subjects per sub-study (See section Statistical Considerations). We will treat each of the four PET/CT system as its own sub-study; however, we will perform each of the first four sub-studies identically other than the manufacturer system-induced differences.

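### Measurement / Instrumentation gives 37 as the required evaluable number per sub-study, but the protocol's own calculation gives 33 evaluable and 37 enrolled

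*Protocol*

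**What the plan says.** The Protocol states the requirement per sub-study in two places in section IV, Procedures.

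- **Sample Size Considerations** gives the derivation. The requirement is: "The project statistician has calculated a required sample size of 33 evaluable subjects per imaging modality". Among the inputs, "we assume that the coefficient of variation (COV) is 12% and the equivalence limit is 10" (per cent). On power at that number, the section states: "we will achieve 80% power in an equivalence test of means using two one-sided tests (TOST) on data from a two-period cross-over design". The significance level is then fixed at 0.025. Drop-out follows: "We assume a drop-out rate of 10% (4 subjects) which leads to our target population of 37 enrolled subjects per unique sub-study".
- **Measurement / Instrumentation**, directly after the primary endpoint, gives a figure without a derivation: "The project statistician has calculated a required sample size of 37 evaluable subjects per sub-study (See section Statistical Considerations". No heading called Statistical Considerations appears in the text. The section that matches is Sample Size Considerations.

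Sample Size Considerations ends with an overall estimate of 204 subjects over six sub-studies.

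The two places use different units, imaging modality and sub-study. For Sub-Studies A to D these are the same, because each PET/CT system is treated as its own sub-study.

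**The concern.** Both statements are credited to the project statistician's calculation, yet one calls 37 the enrolled number and the other calls it the evaluable number. If 10% of patients are expected to be lost, the same figure cannot be both.

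The evaluable number is what a finished sub-study is judged against. The misstatement stands next to the primary endpoint, where a reader would look for the target. If it were followed, more patients would have to be enrolled than the calculation calls for. Each of them would have one additional FDG injection, which the Risks text puts at 4 mSv. If it were not followed, a sub-study that met its design could be reported as short of its stated requirement.

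**Working it through.** **Inputs stated in Sample Size Considerations:** COV 12%, equivalence limit 10%, alpha 0.025, 80% power, TOST, two-period crossover, 33 evaluable, 10% drop-out (4 subjects), 37 enrolled, 204 overall. Sequence allocation is 1:1 (Randomization paragraph).

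**Inputs assumed here, because the protocol does not give them:** a true difference of zero; 12% read as the within-subject COV; alpha 0.025 applied to each one-sided test; the 10% limit read as ±0.10 on the raw scale or 0.90 to 1.10 on the log scale.

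**Step 1. Reproduce 33.** In a 2×2 crossover with N patients in total, SE = s_w × √(2/N) with N − 2 degrees of freedom. Equivalence is declared when the estimate lies at least t × SE inside both limits. On the raw scale at N = 33:

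- SE = 0.12 × √(2/33) = 0.0295
- t(0.975, 31 df) = 2.04, so t × SE = 0.0603
- With the SD treated as known, power is 2Φ((0.10 − 0.0603)/0.0295) − 1, about 0.82. Integrating over the sampling distribution of the variance estimate gives 0.813.

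On the log scale, s_w = √ln(1 + 0.12²) = 0.1196 and the limits are ln 0.90 = −0.105 and ln 1.10 = 0.095. Power by the integrated method:

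| Evaluable N | Raw scale, ±0.10 | Log scale, 0.90 to 1.10 |
|---|---|---|
| 32 | 79.4% | 79.6% |
| 33 | 81.3% | 81.4% |
| 37 | 87.3% | 87.3% |

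Thirty-three is the smallest N that reaches 80%, so the protocol's figure is reproduced as an evaluable number.

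**Step 2. Reproduce 37.** 33/(1 − 0.10) = 36.7, rounded up to 37. Conversely, 37 × 0.90 = 33.3. The figure 37 is the drop-out-inflated enrolment.

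**Step 3. What 37 evaluable would require.**

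- Dividing by 0.90: 37/0.90 = 41.1, rounded up to 42 enrolled. That is 5 more per sub-study and 20 more over A to D.
- Adding 10% of the evaluable number, rounded up: 37 + 4 = 41 enrolled. That is 4 more per sub-study and 16 more over A to D.

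Both conventions turn 33 into 37, so the protocol does not show which was used.

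**Step 4. Does the overall total settle it?** 204/6 = 34. By comparison, 6 × 33 = 198 and 6 × 37 = 222. The total matches neither figure.

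**Step 5. Sensitivity to the assumed inputs, alpha 0.025.**

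| Variant | Power at 33 | Power at 37 |
|---|---|---|
| Log limits 0.90 to 1.11, true difference 0 | 86.8% | 91.5% |
| Log limits 1/1.10 to 1.10, true difference 0 | 76.0% | 83.0% |
| Raw ±0.10, true difference 1.5% | 76% | 82% |

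The percentages move with these choices. Steps 2 and 3 do not depend on them, and neither does the mismatch between the two statements.

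**The case against.** The strongest reply is that this is a slip which the document largely resolves. Measurement / Instrumentation gives no derivation and refers the reader elsewhere. The only sample-size calculation states 33 twice, ties it to 80% power and shows how 37 follows. A reader who finds that section, despite the wrong section name, will see that 37 means enrolled. This stands. It identifies which figure is wrong and keeps the point modest, but the requirement as written is still incorrect.

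The second reply is that the recomputed power rests on unstated inputs. That also stands: the zero true difference and the exact form of the limits are assumptions, and Step 5 shows their effect. The finding does not need them, since the protocol itself assigns 80% to 33.

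A reader might infer more than the text supports, in two ways.

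- *That the protocol gives contradictory rules on replacing drop-outs and on when a sub-study is complete.* It states no rule on either. Enrolled and evaluable targets suggest different conduct, but neither section says that non-completers are or are not replaced, or that enrolment closes at a given count. Silence is not a contradiction.
- *That the recruitment text adds a third enrolment rule.* It does say that "the Principal Investigator's discretion will be utilized regarding the number of patients enrolled and their disease types", but the sentence opens with monitoring the spread across disease categories and gives a representative sample as its purpose. In context it governs the disease mix and sets no evaluable target.

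**Conclusion.** The point holds as a misstated sample size. Measurement / Instrumentation reports 37 as the evaluable requirement, whereas the protocol's calculation gives 33 evaluable and 37 enrolled. Taken literally, the misstatement adds 4 to 5 enrolled patients per sub-study, or 16 to 20 over A to D. It also leaves a sub-study with the planned 10% loss about 4 evaluable patients below one of its two stated targets.

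With a true difference of zero and limits of ±10% or 0.90 to 1.10, power is about 81% at 33 and about 87% at 37, so neither reading puts the stated 80% at risk. No effect on the type I error rate was shown. The arithmetic favours Sample Size Considerations, and a carry-over of the enrolled figure is the likely cause. The overall total of 204 cannot be used to choose between the two and is itself unreconciled.

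**What to change.** 1. In Measurement / Instrumentation, replace 37 evaluable with 33 evaluable (37 enrolled) per sub-study.
2. Point the cross-reference to Sample Size Considerations.
3. Reconcile the overall total of 204 with 37 enrolled per sub-study. If all six sub-studies enrol 37, the total is 222. If a different number is planned for any of them, show how 204 is reached.
4. While the text is open, add the true difference and the exact limits used in the calculation, so that 33 can be reproduced without assumptions.

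Items 1 and 2 are text corrections that need no patients beyond the 37 already planned per sub-study. Item 3 changes the declared total by up to 18 (222 − 204) without changing any sub-study's target. A rule on replacing non-completers would be a separate design decision for the sponsor and is not needed to correct this error.

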For secondary assessments, we will determine by three independent, blinded readers the image quality for a diagnostic interpretation with a linear 10 cm scale from exceptional to unacceptable. We will use the same approach to assess the diagnostic confidence and occurrence of image artifacts and to allow for any additional comments desired. For the read assessment, each PET/CT exam will be individually assessed in a randomized order. Upon completion of this assessment and after a duration of several weeks, a matched pair assessment will be performed to assess equivalency during a side-by-side comparison using the same assessment scales. If those assessments confirm equivalency, we plan to add a full diagnostic read of each exam separately with blinded dosing information.

For this Phase I study, we believe that performing intra-individual comparisons on the same PET/CT system is the only way to get unconfounded, objective assessment of the equivalency of dose reduction. In case we would find difference between the four different PET/CT systems, different dose reduction schemes might be necessary.

While we cannot evaluate in this trial the equivalency for response assessment of therapy between the low dose and current standard of care dose, we do have at least the ability to evaluate that the difference in FDG uptake between the whole body sweep at 60 min +/- 10 min and 75 min +/- 10 min for the target regions is not impacted by dose. While this is our hypothesis we want to evaluate, we will at the same time gain insight into the intra-individual variability in FDG uptake within such a 15 min +/- 10 min window. The current guidelines recommend that the PET/CT whole body sweep be performed 60 min +/- 10 min post injection, giving a 20 min window to start the whole body sweep [Shankar]. Current clinical practice however is favoring imaging around 75 min p.i. which leads to a considerable number of protocol deviations in clinical trials.

As Imaging Core Laboratory for a large number of trials which include PET imaging, we see that the protocol deviation rate in time post injection is consistently the highest with rates of 15% to 40% depending on protocol, most frequently however in the time frame of 70 to 80 min post injection. By adding this aim to the protocol, we can answer another burning clinical/scientific question without adding any additional radiation exposure to the patient.

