All paper and electronic data/information will be coded prior to any review or analysis. All paper documents will be stored in a locked file cabinet with limited access in the Department of Radiology at The Ohio State University. All electronic data obtained through PACS or IHIS will be stored in a coded manner on password protected servers with limited access in the Department of Radiology at The Ohio State University. No individual identities will be used in any publications resulting from this study. Officials from examining bodies such as the U.S. Food and Drug Administration or NIH may inspect records pertaining to this study.

Internal Validity

This crossover design is necessary to blind the patient and the technologist to be unbiased during the performance of the imaging, as motion artifacts, positioning, and other aspects can influence image quality to some extent.

Data Analysis

Our primary hypothesis is that the SUVmax will be equivalent between standard of care dosing (13 mCi) and the low dose (5 mCi) in each PET/CT system. The two one-sided tests procedure (TOST) will be used to test the equivalence of SUVmax at 75 min post injection between the standard care of dosing and the low dose. As SUVmax is known to have lognormal distribution, the data will be log-transformed before all analysis. Holm-Bonferroni method will be used to adjust for multiple ROIs. The McNemar-Bowker's test will be used to evaluate the inter-reader reliability in image quality measured from 1-10 scale between every two readers. The average scores will be calculated among those 3 readers. The TOST test will be used to

test the equivalence in the average score of image quality between the standard care of dosing and the low dose.

The percentage of change in SUVmax measured from 60 min to 75 min will be tested first for equivalence between the standard of care dosing and the low dose target ROI in each PET/CT system. Then the SUVmax measured at 60 min will be compared to SUVmax measured at 75 min within standard care of dosing and the low dosing groups, respectively.

V. Bibliography

- 3. Miletich, RS. Positron emission tomography for neurologists. *Neurol Clin.* Feb 2009;27(1):61-88.

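### Image quality is recorded on a 10 cm line but analysed as a 1-10 scale, and the 12% COV, 10% limit and 80% power stated for it depend on which end of the line is scored zero

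*Protocol*

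**What the plan says.** Measurement / Instrumentation, under the secondary assessments, has three blinded readers judge "the image quality for a diagnostic interpretation with a linear 10 cm scale from exceptional to unacceptable". It names the two anchors but not which end carries the high number. The same approach is used for diagnostic confidence and artifacts. A full diagnostic read is to be added if the reader assessments confirm equivalence.

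Data Analysis describes the measure differently. It uses the McNemar-Bowker test for "inter-reader reliability in image quality measured from 1-10 scale", averages the three readers' scores, and tests that average by TOST. It gives no equivalence limit for the score. It also says that the data will be log-transformed before all analysis, and the only reason given is the distribution of SUVmax.

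Sample Size Considerations states that 33 evaluable subjects are required "if we assess tracer uptake (FDG) using both a quantitative (SUVmax) and a visual quality assessment". It then assumes that "the coefficient of variation (COV) is 12% and the equivalence limit is 10" per cent. The 80% power is for TOST "on data from a two-period cross-over design", "using an alpha level of 0.025 (0.05/2) after Bonferroni adjustment each system, respectively". No separate variability or limit is given for the visual score. Measurement / Instrumentation ties the 10% by name only to SUVmax, the primary endpoint.

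**The concern.** There are two linked problems.

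First, the instrument is not settled. A continuous 10 cm line and a 1-10 scale have different minimum values and call for different agreement statistics. McNemar-Bowker tests symmetry in a table of matched categories, so it has no direct input from a continuous line.

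Second, a COV and a percentage limit make sense for a quantity with a true zero, such as SUVmax. On a line with two labelled ends, zero is a convention. Reversing the line leaves the images and the differences in cm unchanged, but it changes the mean, and with it the COV and 10% of the mean.

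At stake is whether image-quality equivalence would be judged by what loss of quality matters or by a scoring convention, and whether the stated power applies to this measure at all. The reader assessments are also the closest evidence the trial has for the Overview's aim of lowering the dose without affecting diagnostic ability.

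**Working it through.** **Inputs from the protocol.** N = 33 evaluable; two-period crossover with TOST; alpha 0.025 per one-sided test; COV 12%; limit 10%; line length 10 cm.

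**Inputs assumed.** The protocol gives no mean or SD for the visual score. I use mean scores of 2 to 5 cm from the exceptional end and within-patient SDs of 0.5 and 0.96 cm.

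**1. Reproducing N = 33.** Take the 12% and 10% as percentages of the same mean, with a true difference of zero.
- SE = SDw × √(2/N) = 0.12 × √(2/33) = 0.0295.
- With t(0.975, 31 df) = 2.04, t × SE = 0.060.
- Treating the SE as known, power ≈ 2Φ((0.10 − 0.060)/0.0295) − 1 ≈ 0.82. Integrating over the variance estimate gives 0.813, and 33 is the smallest N that reaches 80%.
- On the log scale with limits 0.90 to 1.10, N is again 33 (power 0.814).

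So the stated figures work as a mean-relative pair.

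**2. Reversing the line.** Replace a score x by 10 − x. The mean m becomes 10 − m and the SD s is unchanged.
- The 10% limit changes from 0.1m to 0.1(10 − m).
- The COV changes from s/m to s/(10 − m).
- Each pair agrees only at m = 5 cm.

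At m = 2 cm from the exceptional end, the limit is 0.2 cm from that end and 0.8 cm from the other. An SD of 0.96 cm is a COV of 0.96/2 = 48% from one end and 0.96/8 = 12% from the other.

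**3. One set of results scored both ways.** Suppose N = 33, a standard-dose mean 2 cm from the exceptional end, low dose 0.3 cm worse, and an SD of paired differences of 0.6 cm.
- Half-width = 2.04 × 0.6/√33 = 0.21 cm, so the interval runs from 0.09 to 0.51 cm.
- Scored from the exceptional end (limit 0.2 cm): not equivalent.
- Scored from the unacceptable end (limit 0.8 cm): equivalent.

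**4. Power at zero true difference, limit 10% of the mean.**

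| Mean from exceptional end | SDw | Zero at exceptional | Zero at unacceptable |
|---|---|---|---|
| 2 cm | 0.5 cm | 0.005 | 1.00 |
| 3 cm | 0.5 cm | 0.317 | 1.00 |
| 4 cm | 0.5 cm | 0.765 | 0.994 |
| 5 cm | 0.5 cm | 0.952 | 0.952 |
| 2 cm | 0.96 cm | 0.000 | 0.813 |
| 3 cm | 0.96 cm | 0.000 | 0.637 |
| 4 cm | 0.96 cm | 0.009 | 0.385 |
| 5 cm | 0.96 cm | 0.122 | 0.122 |

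If the COV is 12% in the direction actually used, SD/limit = 0.12m/0.10m = 1.2 and power is about 0.81 whatever m is. The same images can have a 12% COV in both directions only at m = 5 cm.

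**5. A limit in cm.** A fixed limit on the paired difference gives the same result in either direction. With an illustrative limit of 1.0 cm and SDw 0.96 cm, power is 0.967 both ways. More generally, N = 33 keeps about 81% power if the within-patient SD is at most 1.2 times the limit.

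**The case against.** The strongest reply is that the protocol never states a limit for the image-quality TOST. Data Analysis gives none, the only named endpoint tied to 10% is SUVmax, and the margin of a secondary endpoint is commonly left to the analysis plan, which is not shown. That stands in part: applying 10% to the mean score is an inference. But Sample Size Considerations names the visual assessment as part of the basis for N and power and gives no other figures. The conflict over the instrument is also in the protocol itself.

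Several stronger readings are tempting, and the document does not support them.
- **Direction always changes the verdict.** It can do so only if the 10% is relative to the mean score and scores lie away from mid-line. If 10% meant 10% of the line (1 cm), direction would not matter. The protocol does not say so, and the power claim would then need an SD in cm.
- **Power is about zero.** The contrast of 0.000 with 0.813 pairs an assumed SD of 0.96 cm with a mean of 2 cm. That is a 48% COV, four times the protocol's figure.
- **The line is scored from the exceptional end, so the criterion is strictest for the best images.** The wording orders the anchors but does not set the zero, and TOST on a group mean has one limit for the sample, not one per image.
- **The average-score test alone decides whether the diagnostic read is added.** The condition refers to the reader assessments together, including confidence, artifacts and the side-by-side comparison, and the read is an addition to the trial's primary conclusion.

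**Conclusion.** The point holds in a limited form. Without any assumption, the protocol describes one measure as two different instruments and pairs a continuous line with a categorical reader test. It also extends to that measure a power statement whose figures are percentages of a mean. Those figures have no direction-free meaning on a bounded line, so the 80% power is unsupported for image quality; it has not been shown to be wrong.

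The effect on the verdict is conditional. If 10% of the mean score is the criterion and scores lie away from mid-line, the same images can pass or fail by scoring direction. With a mean 2 cm from the exceptional end, the limits differ fourfold (0.2 against 0.8 cm). The means and SDs used to show this are assumptions; at mid-line the difference vanishes.

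The measure is secondary. The SUVmax test and its N = 33 are unaffected. This should be corrected, and the correction is cheap.

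**What to change.** - **Measurement / Instrumentation and Data Analysis:** describe one instrument with a stated direction, for example a 0 to 10 cm line with 0 = unacceptable and 10 = exceptional. Carry the wording over to diagnostic confidence and artifacts, which use the same approach.
- **Equivalence limit:** give an absolute limit in cm on the paired difference in the three-reader mean, justified by the sponsor as the largest quality loss that does not matter. A limit of ±1 cm is only an illustration and has no basis in the protocol.
- **Transformation:** analyse the score untransformed and limit the log-transformation sentence to SUVmax.
- **Reader agreement:** replace McNemar-Bowker with a measure for continuous scores, such as an intraclass correlation coefficient. Keep it only if the score is made categorical.
- **Sample Size Considerations:** confine the 12%, 10% and 80% statement to SUVmax, or restate power for image quality with a within-patient SD in cm and the chosen limit.

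The cost is protocol wording and the reader form, with no added patients or data. The downside is that no 80% power can be claimed for image quality until an SD in cm is supplied.
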